Appendix 4. Definition of Diabetes Mellitus at Baseline

A subject is considered having diabetes mellitus at baseline of the qualifying study, if any of the conditions below is met:

- Subject had a diagnosis of diabetes mellitus recorded on the “CARDIOVASCULAR RISK FACTORS” CRF or on the “SIGNIFICANT MEDICAL HISTORY AND NON-DRUG ALLERGIES” CRF at screening;
- Subject received any drug treatment taken on Day 0 recorded on the “CONCOMITANT DRUG TREATMENT - ANTI-DIABETIC” CRF;
- Subject’s HbA1c $\geq 6.5\%$ at baseline or, if HbA1c is not available, baseline fasting plasma glucose ≥ 126 mg/dL.

Appendix 5. Handling of Joint Count Assessment (Missing Assessment, “NOT DONE” and “NOT APPLICABLE”) and Injected Joint

This Section applies to the tender/painful joint (68) and swollen joint (66).

For missing or “NOT DONE” assessment:

- A missing painful / tender assessment or one “NOT DONE” at baseline is set to “not painful / tender”;
- A missing swollen assessment or one “NOT DONE” at baseline is set to “not swollen”;
- A missing painful / tender assessment or one “NOT DONE” post-baseline is set to “painful / tender”;
- A missing swollen assessment or one “NOT DONE” at post-baseline is set to “swollen”.

For “NOT APPLICABLE” assessment:

- A joint marked “NOT APPLICABLE” is not to be counted in the summation of swollen and painful / tender joints at baseline and post baseline;
- Any new “NOT APPLICABLE” for a joint post baseline is set to “painful / tender” and “swollen”. That is, if a joint is assessed, “Present”, “Absent”, “NOT DONE”, or with missing assessment at baseline, the same joint marked as “NOT APPLICABLE” post-baseline will be counted as “painful / tender” and “swollen”.

If a joint received an intra-articular injection (baseline or post-baseline), then set the joint status to “painful/tender” and “swollen” on and after the date of injection.

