9.1. Sample Size Determination

This is an estimation study. The primary objective will be met by estimating the effect of each treatment and their difference. A sample size of 90 subjects per group was selected such that the 2-sided 95% confidence interval (CI) half-width for the difference in Δ HAQ-DI at Month 6 between tofacitinib 5 mg BID + placebo and tofacitinib 5 mg BID + MTX would be approximately 0.18 assuming a common standard deviation (SD) of 0.6 for both groups. Similarly this sample would yield a 2-sided 95% CI half-width of approximately 0.47 for the difference in Δ PASDAS at Month 6 between the 2 treatment groups assuming a common SD of 1.6 for both groups.

No adjustment for multiple comparisons will be made in the analyses. Nominal statistical significance will be claimed if the 2-sided p value is ≤ 0.05 .

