9.3.1. Analysis of Primary Endpoints

There are two primary endpoints in the sub-study: Δ HAQ-DI at Month 6 and Δ PASDAS at Month 6. Each primary endpoint will be analyzed using a MMRM without imputation for missing values on the FAS.

To assess the impact of missing data due to dropouts, the SAP will also specify additional analyses to assess the sensitivity of the primary analysis to departures from the assumed missing data mechanism.

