6. HANDLING OF MISSING VALUES

For the SF-36v2, EQ-5D-3L and FACIT-F instruments, the same approaches as for the main LTE study will be followed. Refer to main LTE study [Section 7](#) for the details. In general, missing values will not be imputed. For the binary efficacy endpoints (eg, PsARC Response), missing responses will be treated as non-response (MR=NR).

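### The SAP's only joint-level rule scores an unexamined joint as inactive at baseline and active afterwards; on the natural reading it governs the methotrexate-withdrawal sub-study, where it pushes change toward worsening

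*SAP*

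**What the plan says.** SAP Appendix 5 handles single joints. Before treatment, "A missing painful / tender assessment or one “NOT DONE” at baseline is set to “not painful / tender" and "A missing swollen assessment or one “NOT DONE” at baseline is set to “not swollen". After baseline the direction reverses: "A missing painful / tender assessment or one “NOT DONE” post-baseline is set to “painful / tender" and "A missing swollen assessment or one “NOT DONE” at post-baseline is set to “swollen". A joint that becomes NOT APPLICABLE only after baseline is also counted as tender and swollen. The scope sentence is "This Section applies to the tender/painful joint (68) and swollen joint (66"; it neither limits the rule to the long-term extension (LTE) nor names the sub-study.

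SAP Appendix 6 holds the sub-study analyses. It takes PASDAS, PsARC, MDA and the ACR components from SAP Appendix 2, and all of these use the 68/66 counts. It sets baseline as the latest value before the first sub-study dose, and never cites Appendix 5. On missing data, its Section 6 says "In general, missing values will not be imputed". Protocol Appendix 10, Section 9.3.1, says "Each primary endpoint will be analyzed using a MMRM without imputation for missing values on the FAS". Section 9.1 of the same appendix sets the target: "The primary objective will be met by estimating the effect of each treatment and their difference".

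**The concern.** Counting an unexamined joint against the subject is conservative when the endpoint is improvement, as with ACR20 in the LTE. The sub-study asks a different question: do subjects hold their disease control once methotrexate is withdrawn? There, change toward worsening is the outcome under study, and both halves of the rule add to it. An active joint missed at the switch visit lowers the starting count, and an inactive joint missed later raises the follow-up count.

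The planned targets include the change in each arm as well as the difference. The per-arm estimates of PASDAS and joint counts therefore shift even if incomplete examinations are equally common in both arms. Responder endpoints can also flip, because MDA has joint-count thresholds of 1 and PsARC allows no worsening in any measure.

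**Working it through.** **Inputs.** PASDAS joint terms (SAP Appendix 2.9): 0.101 × ln(swollen + 1) and 0.048 × ln(tender + 1), with the whole score multiplied by 1.5. Planning figures (Protocol Appendix 10, Section 9.1): 90 per arm, SD 1.6, half-width about 0.47. Assumed, because the documents give no figure: the number k of unexamined joints and the share of subjects affected.

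**1. Planned precision.** 1.96 × 1.6 × √(2/90) = 0.467, which matches the stated 0.47.

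**2. One stable subject.** Let true counts S (swollen) and T (tender) stay constant. Suppose k joints, truly inactive, are not examined for either sign at a later visit. Each count rises by k, and

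false PASDAS change = 1.5 × [0.101 × ln((S+k+1)/(S+1)) + 0.048 × ln((T+k+1)/(T+1))].

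| True S/T | k = 2 | k = 4 |
|---|---|---|
| 0/0 | 0.246 | 0.360 |
| 1/1 | 0.155 | 0.246 |
| 3/6 | 0.080 | 0.138 |
| 5/10 | 0.056 | 0.100 |

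For 1/1 and k = 4: 1.5 × (0.101 + 0.048) × ln(6/2) = 0.2235 × 1.0986 = 0.246.

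**3. The baseline half.** With true counts 3/6, joints that are both tender and swollen but missed only at the switch visit give a false rise of 0.055 (1 joint) or 0.250 (3 joints).

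**4. Arm mean.** Shift = share affected × change per affected subject. If 10% of subjects miss 4 joints from 1/1: 0.10 × 0.246 = 0.025 in PASDAS, about 5% of the half-width (0.025/0.467). The mean tender and swollen counts each rise by 0.10 × 4 = 0.4.

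**5. Arm difference.** Bias = difference between arms in the share affected × change per affected subject. It is zero if the shares are equal. For the same subject type, a gap of 5 to 20 percentage points gives 0.05 × 0.246 = 0.012 to 0.20 × 0.246 = 0.049, or roughly 3% to 11% of the half-width.

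**6. Responder endpoints.** MDA (SAP Appendix 2.8) needs at least 5 of 7 criteria, two of which are a tender and a swollen count of at most 1. From 0/0, two unexamined joints fail both. A subject meeting all 7 still has 5 and keeps MDA; a subject meeting 6 or 5, both joint criteria included, drops to 4 or 3 and loses it. For PsARC, SAP Appendix 2.1 sets any rise from a baseline of 0 to 999999%, so one unexamined joint after a zero count would read as worsening.

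**7. One joint, two scores.** The Switch/Baseline visit is also LTE Month 24, 27, 30, 33 or 36 (Protocol Appendix 10, Section 6.1). A joint not done that day is post-baseline for the LTE, hence active, and baseline for the sub-study, hence inactive.

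**8. Effect of a symmetric rule.** Scaling the count to the joints examined, for the stable subject of step 2, gives a false PASDAS change of 0.00 at 0/0. For counts up to 5/10 it gives at most 0.012 for 4 unexamined joints and at most 0.032 for 10.

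**The case against.** The strongest reply is that nothing says Appendix 5 applies. SAP Section 2 places sub-study analyses in Appendix 6, which cites parts of Appendix 2 repeatedly and Appendix 5 never. The amendment list dates Appendix 5 to Version 3 and the sub-study to Version 4. This stands in part: application is an inference. But if Appendix 5 does not apply, no text says how one unexamined joint enters a sub-study count, so an edit is needed either way.

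A reader might infer that the rule contradicts the no-imputation statements. The documents do not support that. Those statements concern missing endpoint values, and they sit beside item-level rules elsewhere: HAQ-DI averages non-missing domains, FACIT-F is prorated, and SF-36 substitutes item means. SAP Section 7 draws the same line for the LTE. Proration would breach the wording too if it were read so strictly.

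A reader might also set 0.155 to 0.360 beside 0.47 and conclude that the primary comparison is at risk. Those are single-subject shifts, whereas 0.47 is a half-width for a difference in means. Methotrexate assignment is randomised and blinded, and assessors are blinded, which favours balance. Balance is not assured: subjects may be discontinued for deterioration, and an early-termination visit takes precedence within its window (SAP Appendix 6, Section 7.4). Whether incomplete examinations cluster at such visits is unknown.

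Finally, the worsening is false only where the unexamined joint was truly inactive, or was active and missed at the switch visit. Joints that are artificial or absent from the start are recorded as not applicable and excluded. A wholly missed examination is a doubtful case, because Appendix 5 is worded joint by joint and SAP Appendix 2.9 makes PASDAS missing when a component is missing.

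**Conclusion.** The concern holds as a specification gap with a known direction. On the natural reading, the SAP puts one-directional false worsening into the sub-study's joint counts, PASDAS, PsARC and MDA, and therefore into per-arm estimates that the plan names as targets. HAQ-DI is unaffected. Per-subject PASDAS shifts are 0.155 to 0.360 for 2 to 4 inactive unexamined joints at counts of 0/0 or 1/1, and smaller at higher counts. The arm-mean shift is about 0.025 under an assumed 10% of subjects missing 4 joints from 1/1. The documents give no frequency of unexamined joints, so the true size is unknown.

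They do not support saying that the treatment difference is biased, which requires imbalance between arms, or that any subject with two unexamined joints loses MDA, which happens only to those meeting 5 or 6 of the 7 criteria.

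**What to change.** In SAP Appendix 6, state the joint rule for the sub-study and make it identical at the switch visit and at every later visit. One workable form is proration over applicable joints: count × applicable joints / joints examined. The count is set to missing below a prespecified minimum number examined; half is a reasonable choice, but the cut-off is a preference. Treat a newly NOT APPLICABLE joint as not examined; otherwise part of the asymmetry remains. Keep Appendix 5 for the LTE, whose change endpoints also need a joint rule. Report unexamined joints by arm and visit, so that balance can be seen.

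The injected-joint passages must also be reconciled. SAP Appendix 5 scores such joints as tender and swollen from the injection onward. Protocol Sections 7.2.1 and 7.2.3 use pre-injection status. Protocol Appendix 6 gives pre-injection status and also says not to count them.

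The cost is SAP wording and one derivation, with no new data. The downside is that joint counts are derived differently in the LTE and the sub-study.

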Appendix 6. Methotrexate Withdrawal Sub-Study

1. INTRODUCTION

The purpose of this sub-study is to assess the efficacy, safety and tolerability of tofacitinib 5 mg BID administered as monotherapy after methotrexate (MTX) withdrawal compared to tofacitinib 5 mg BID continued in combination with MTX in subjects with active PsA. Subjects who have completed at least 24 months of participation in the long term extension study A3921092 and are currently receiving methotrexate may be included.

Subjects will be randomized to the 2 treatment arms in a 1:1 ratio, one in which they will receive open label tofacitinib 5 mg tablets BID and blinded methotrexate capsules (oral dose range from 7.5 mg to 20 mg per week) and the second in which they will receive open label tofacitinib 5 mg tablets BID and blinded MTX placebo capsules. The sub-study will be approximately 12 (standardized 4-week) months in duration and visits will occur at Baseline, Months 1, 3, 6, 9 and 12. The sub-study baseline will occur at the same time as a scheduled study visit at or after Month 24 of A3921092. This visit will be referred to as Sub-study Switch Visit or Baseline visit (Sub-study Switch/Baseline visit).

1.1. Study Design

This sub-study within Study A3921092 is a Phase 3, randomized, double-blind, placebo-controlled, parallel group estimation study designed to assess the efficacy, safety and tolerability of tofacitinib 5 mg BID versus tofacitinib 5 mg BID in combination with concomitant MTX in subjects with active PsA. Subjects with active PsA will have previously completed at least 24 months of treatment with tofacitinib in Study A3921092 and will be on a stable dose of tofacitinib 5 mg BID for at least 3 months prior to the first dose of sub-study drug and be on a stable dose of oral MTX at least 4 weeks prior to the first dose of sub-study drug. For subjects who are qualified to enter into the sub-study, the Combined A3921092 Sub-study Switch/Baseline visit will occur at a scheduled study visit at or after Month 24 of A3921092. There will be no separate Baseline visit for the sub-study. The visit window will remain as in the LTE in which a month is considered 28 days. Once a subject enters the sub-study, they will complete their participation in the sub-study portion and be unable to re-enter the main study. Subjects may be discontinued from the sub-study at any time during the sub-study in the event of deterioration of response as determined by the investigator.

Eligible subjects from study A3921092, will be randomized into A3921092 sub-study in a 1:1 ratio to tofacitinib 5 mg BID + MTX placebo or tofacitinib 5 mg BID + MTX. MTX will be blinded to the subjects, investigator and the sponsor. The subjects in the tofacitinib 5 mg BID + MTX group will receive blinded MTX capsules (range dose of 7.5-20 mg a week based upon the pre-existing dose) and the subjects in the tofacitinib 5 mg BID group will receive the matching MTX placebo capsules. For the duration of the sub-study tofacitinib dose must remain stable at 5 mg BID. The MTX dose and oral route of administration must remain stable for the 12 month duration of the sub-study. All subjects will receive open-label tofacitinib 5 mg BID throughout the sub-study without dose increase. The total number of subjects randomized will be approximately 180 with 90 in each treatment group. Treatment duration for subjects participating in this sub-study is approximately 12 months.

At various time points in this trial, safety measurements, including physical examination, clinical laboratory tests, adverse event monitoring, electrocardiograms (ECGs) and vital signs will be performed. All subjects will be monitored for clinical evidence of PsA response to treatment. Health Outcomes Measures (ie, Patient Reported Outcomes assessments for pain, quality of life, physical function, fatigue and health status) will also be performed at various time points in this trial. In addition, subjects will be monitored for serious infections, lymphadenopathy and lymphoproliferative disorder (LPD).

1.2. Study Objectives

Primary Objective

- *To assess the efficacy of tofacitinib 5 mg BID monotherapy as compared to tofacitinib 5 mg BID with background MTX in subjects who have received prior treatment of tofacitinib in combination with MTX.*

Secondary Objective

- *To assess the safety and tolerability of tofacitinib 5 mg BID monotherapy as compared to tofacitinib 5 mg BID with background MTX in subjects who have received prior treatment of tofacitinib in combination with MTX.*

2. INTERIM ANALYSES, FINAL ANALYSES AND UNBLINDING

No formal interim analysis is planned for the sub-study. However, data-cuts may be performed as needed to support tofacitinib regulatory submission.

This sub-study will use the same External Data Monitoring Committee (E-DMC) as for the main LTE study.

A final analysis will occur when all subjects finish the sub-study or terminate early.

3. HYPOTHESES AND DECISION RULES

3.1. Statistical Hypotheses

There are no formal hypotheses being tested in this sub-study.

3.2. Statistical Decision Rules

There are no statistical decision rules in this sub-study.

4. ANALYSIS SETS

Below is a description of the Analysis Sets defined for this sub-study.

4.1. Full Analysis Set

The full analysis set (FAS) is defined as all subjects who are randomized to the sub-study and receive at least one dose of the sub-study drug (tofacitinib, MTX or placebo). Subjects will be analyzed based on treatment randomized.

4.2. ‘Per Protocol’ Analysis Set

There is no Per Protocol Analysis Set defined for this sub-study.

4.3. Safety Analysis Set

The safety analysis set (SAS) is defined as all subjects who received at least one dose of the sub-study drug (tofacitinib, MTX or placebo). Subjects will be analyzed based on treatment received.

4.4. Other Analysis Sets

4.4.1. Endpoint Specific Analysis Sets

Subjects will be excluded from FAS for analyzing a specific endpoint if the criterion for inclusion is not met for the endpoint as described in **Table 3 Endpoint Specific Analysis Sets**.

Table 3 Endpoint Specific Analysis Sets

Instrument/Endpoint	Inclusion	Rationale
Δ PGA-PsO	Include subjects with baseline PGA-PsO>0	PGA-PsO=0 means no PsO disease at baseline as measured by PGA.
Δ BSA	Include subjects with baseline BSA>0	BSA=0 means no PsO disease at baseline as measured by BSA.
Δ DSS	Include subjects with baseline dactylitis severity score (DSS)>0	Baseline DSS=0 means absence of dactylitis. Dactylitis is not an enrollment criterion so it is expected that only a subset of the subjects will have dactylitis at baseline.
Dactylitis presence	Include subjects with baseline DSS>0	Baseline DSS=0 means absence of dactylitis. Dactylitis is not an enrollment criterion so it is expected that only a subset of the subjects will have dactylitis at baseline.
Δ Leeds Enthesitis Index (Δ LEI)	Include subjects with baseline LEI>0	Baseline LEI score=0 means absence of enthesitis as measured by LEI. Enthesitis is not an enrollment criterion so it is expected that only a subset of the subjects will have enthesitis at baseline.
Enthesitis presence	Include subjects with baseline LEI>0	Baseline LEI score=0 means absence of enthesitis as measured by LEI. Enthesitis is not an enrollment criterion so it is expected that only a subset of the subjects will have enthesitis at baseline.

Abbreviations: Δ =Change from baseline; baseline is the value obtained prior to the first dose of the sub-study; BSA = body surface area; DSS = Dactylitis Severity Score; PGA-PsO = Physician’s Global Assessment of Psoriasis.

4.5. Treatment Misallocations

If a subject was:

- Randomized but not treated, then the subject will appear on the subject evaluation table as randomized but not treated; this is the extent of how much data for this subject will be reported.
- Treated but not randomized, then by definition the subject will be excluded from the FAS and SAFETY analysis sets. A narrative will be provided for this subject in the clinical study report (CSR).

- Randomized but took the incorrect treatment exclusively through the entire duration of the study, then the subject will be reported under the randomized treatment group for the efficacy analysis but will be reported under the treatment they actually received for all safety analyses.
- Randomized but took at least one dose of randomized treatment and one dose of incorrect treatment, then the subject will be reported under the randomized treatment group for the efficacy and safety analyses.

Patient-reported outcomes (PRO) will be considered the same as for efficacy in this regard.

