7.6. Safety

Safety will be assessed by the spontaneous reporting of adverse events (AEs), physical examinations and clinical laboratory results in all subjects who receive at least one dose of study drug. Investigators and Pfizer clinicians will review individual subject data throughout the conduct of the study to ensure the subjects' well-being.

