9.4. Safety Analysis

The safety analysis set (SAFETY) will include all subjects who received at least one dose of the sub-study drug (tofacitinib, MTX or placebo).

For the safety analyses, the baseline will be the latest value obtained prior to the first dose of the sub-study.

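### The sub-study misallocation rule removes treated-but-not-randomized subjects from the safety set, contradicting the dosing-only definitions of that set

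*SAP*

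**What the plan says.** Three places in SAP Appendix 6 and two in protocol Appendix 10 bear on this.

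- **FAS, SAP Appendix 6 Section 4.1:** "all subjects who are randomized to the sub-study and receive at least one dose of the sub-study drug (tofacitinib, MTX or placebo"). Both randomization and a dose are required.
- **Safety set, SAP Appendix 6 Section 4.3:** "The safety analysis set (SAS) is defined as all subjects who received at least one dose of the sub-study drug (tofacitinib, MTX or placebo"). The section adds: "Subjects will be analyzed based on treatment received". Randomization is not mentioned.
- **Safety set, protocol Appendix 10 Section 9.4:** "The safety analysis set (SAFETY) will include all subjects who received at least one dose of the sub-study drug (tofacitinib, MTX or placebo"). Again a dose is the only condition.
- **Safety assessment, protocol Appendix 10 Section 7.6:** safety is assessed "in all subjects who receive at least one dose of study drug".
- **Misallocation rule, SAP Appendix 6 Section 4.5, second bullet:** "Treated but not randomized, then by definition the subject will be excluded from the FAS and SAFETY analysis sets". The next sentence reads: "A narrative will be provided for this subject in the clinical study report (CSR").

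SAP Appendix 6 Section 7.2 assigns the sub-study safety analysis to the safety set. Section 7 of that appendix reports by two groups only: tofacitinib with methotrexate placebo, and tofacitinib with methotrexate.

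**The concern.** The rule in Section 4.5 presents itself as a consequence of the set definitions, and for the safety set it is the opposite of what they say. A programmer building the sub-study safety population cannot satisfy both Section 4.3 and Section 4.5 for a subject who was dosed without being randomized.

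At stake is the composition of the sub-study safety tables. Comparative safety and tolerability is the sub-study's secondary objective, and adverse-event incidence is among its secondary endpoints. A narrative describes a case but adds nothing to a numerator or a denominator. If the conflict is left open, someone will have to choose the reading after such a subject's events are known.

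**Working it through.** No sample size, power or alpha figure is involved, so the check is a comparison of definitions. Take a subject who received at least one dose of sub-study drug and was not randomized.

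| Source | Condition for inclusion | This subject |
|---|---|---|
| SAP App. 6 Section 4.1 (FAS) | randomized and dosed | out |
| SAP App. 6 Section 4.3 (safety set) | dosed | in |
| Protocol App. 10 Section 9.4 (safety set) | dosed | in |
| SAP App. 6 Section 4.5 on the FAS | not randomized, so excluded | out, consistent |
| SAP App. 6 Section 4.5 on the safety set | not randomized, so excluded | out, **contradicts** Section 4.3 and protocol 9.4 |

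The different labels do not explain this. SAP Section 4.3 abbreviates the set as SAS and Section 4.5 calls it SAFETY, but Appendix 6 defines only one safety set, and the protocol attaches the SAFETY label to the same dosing-only definition.

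**Does the subject disappear from all safety tables?** No.

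- SAP Section 8 and Section 8.2.1 put all sub-study data into the cumulative safety analysis of the long-term extension (LTE).
- The LTE safety set equals the LTE FAS (SAP Section 5.3), which requires entry from a qualifying study and one dose of open-label drug (Section 5.1).
- Sub-study entry requires at least 24 months of LTE tofacitinib (protocol Appendix 10 Section 4.1, criterion 3), so the subject is already in that set.
- The LTE display is a single flexibly dosed cohort (SAP Section 8.2). It therefore keeps the events but does not stand in for the sub-study comparison by arm.

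**Size, as an illustration only.** The planned arm is 90 subjects (protocol Appendix 10 Section 3), so one subject is 1/90 = 1.1%. Suppose an arm has *k* subjects with a given event out of 90, and the omitted subject belongs to that arm and had the event. Including the subject changes the arm percentage by (k + 1)/91 − k/90 = (90 − k)/8190.

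- k = 0: 90/8190 = 1.10 percentage points.
- k = 9 (assumed 10% incidence): 81/8190 = 0.99 points.
- k = 45 (assumed 50% incidence): 45/8190 = 0.55 points.

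If the subject did not have the event, the change is k/91 − k/90 = −k/8190, which at k = 9 is −0.11 points. A subject who took sub-study tofacitinib but no capsules belongs to neither arm, and then no arm percentage moves.

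**The case against.** The strongest reply is that this is an editorial slip with safeguards around it. Most of that stands.

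- **Nothing is concealed.** Section 4.5 requires a narrative for each such subject, and the cumulative LTE analysis counts the events. A reader might infer that these adverse events drop out of the trial's safety reporting altogether. The documents do not support that. Only the sub-study tables are affected.
- **The case should be rare.** Under protocol Appendix 10 Section 5.1 the interactive response system supplies the randomization number together with the container numbers. Sections 6.1.1 to 6.1.3 list randomization ahead of dispensing at every entry visit. Because open-label tofacitinib counts as sub-study drug, a reader might infer a ready route to dosing without randomization. The documents describe no route that bypasses the system, so a site error of this kind is hypothetical.
- **Analysis by treatment received is in the SAP only.** A reader might take it as a protocol requirement too, but protocol Appendix 10 Section 9.4 is silent on it.
- **Keeping non-randomized subjects out of a randomized comparison is defensible.** That is true as a design preference, and sub-study safety is descriptive with no formal hypotheses. But Section 4.5 does not state a preference. It claims to follow from a definition that says the reverse.

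Protocol Appendix 10 Section 9 lets the SAP modify the protocol, but that does not resolve the matter. The SAP's own Section 4.3 retains the protocol definition, so the SAP conflicts with itself.

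**Conclusion.** The inconsistency is real and limited to the sub-study safety set. The exclusion is right for the FAS and wrong for the safety set as both documents define it. Applied literally, it would omit a dosed subject's events from the sub-study safety tables and leave a narrative there in their place.

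The importance is minor. The primary endpoints and the cumulative LTE safety analysis are untouched. The figure of about 1 percentage point per subject assumes an uncommon event and a subject who can be placed in an arm of 90. It is not an estimate of bias, because the documents give no expected number of such subjects and it may well be zero. The case for acting is that the SAP foresaw the situation and wrote a rule for it, and that rule should agree with the definition it cites.

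**What to change.** Replace the second bullet of SAP Appendix 6 Section 4.5 with:

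> *Treated but not randomized: excluded from the FAS; included in the Safety Analysis Set under the treatment actually received, or displayed in a separate non-randomized column or listing if neither MTX nor placebo capsules were taken; a narrative will also be provided.*

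The provision for a separate display is needed because a subject who took only sub-study tofacitinib fits neither of the two reporting groups in Appendix 6 Section 7.

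If the sponsor does intend the exclusion, the alternative is to add a randomization condition to the safety set in both SAP Appendix 6 Section 4.3 and protocol Appendix 10 Section 9.4. That touches two documents and narrows the safety population, so the first option is simpler. It costs one bullet of SAP wording, with a column or listing to program only if such a subject occurs, and should be settled before the final sub-study analysis.
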